**Table 2. Probability Profile of Low, Mild and High Scenario**

Dosing Strength	Probability of DLT		
	Low MTD	Mid MTD	High MTD
█	0.2	0.1	0.01
	0.3	0.2	0.05
	0.3	0.2	0.05
	0.4	0.3	0.1
	0.5	0.4	0.2
	0.6	0.5	0.3

For each dosing profile, █ simulated trial data was generated and the BLMR model was used to guide the dose escalation. The simulation results are summarized in [Table 3](#)

**Table 3. Summarized Simulation Results for BLMR**

	Low MTD	Mid MTD	High MTD
N	14.8 (6, 21)*	19.7 (18, 24)	23.0 (24, 24)
MTD dose	129.1 (█)	200.4 (█)	416.8 (█)
% select acceptable MTD	50.6%	62.2%	86.8%
% all dose too toxic	39.2%	12.0%	0%
Study # of DLTs	4.1 (3, 5)	4.2 (4, 5)	2.8 (2, 4)
Study prob. of DLT	33.1%	23.3%	11.9%

\* all continuous data in this table is reported in mean (Q1, Q3)

**Appendix D. Disease Related Events Table**

Organ System	Disease Related Event
Skin	Scleroderma (superficial or fasciitis), lichen planus, vitiligo, scarring alopecia, hyperkeratosis pilaris, contractures from skin immobility, nail bed dysplasia
Mucous membranes	Lichen planus, non-infectious ulcers, corneal erosions/non-infectious conjunctivitis, xerostomia, keratoconjunctivitis sicca
GI tract	Esophageal strictures, steatorrhea, anorexia, malabsorption, weight loss, abdominal pain
Liver	None
GU tract	Vaginal stricture, lichen planus
Musculoskeletal /Serosa	Non-septic arthritis, myositis, myasthenia, polyserositis, contractures from joint immobilization
Hematologic	None
Lung	Bronchiolitis obliterans

[figure not shown]

## Appendix G. Analytical Windows

The last visit with non-missing assessment prior to first dose will be defined as a baseline visit (unless specified otherwise) and the analysis visit name will be “Baseline”. For any visit up to Day 1 pre-dose which is not a baseline visit, the analysis visit will be ‘Pre-Analysis’. For Day 1 post-dose visits, and safety follow-up visit, the analysis visit will be same as the scheduled visit. For any unscheduled visit post safety follow-up visit, the analysis visit will be considered as safety follow-up visit. For post-dose assessments on Day 29 (the day corresponding to Week 4 dosing) and Day 113 (the day corresponding to week 16 dosing), the analysis visit will be same as the scheduled visit. Remaining visits (scheduled visit, unscheduled visit, progressive disease visit, or end of treatment visit) after Day 1 for any assessment will be mapped to the analysis visit based on visit windows defined in the tables below for that assessment. Only visits applicable for that assessment and phase of the study as per the Schedule of Activities tables in the study protocol will be considered for analysis.

Data collected through central lab and local lab will both be mapped into analysis visit windows. The local lab data can only be used in analysis when there is no central lab data available in the analysis visit window.

If more than one visit with non-missing data falls within an analysis visit window, the visit closest to the target day will be considered for analysis. If two visits are equidistant from the target day, the latest visit (or time if on the same day) will be considered. If more than one evaluation has same date and time (for chemistry, hematology or pharmacodynamics results), the value with the smallest accession number will be considered.

Analysis visit windows for selected assessments are included in tables below. For remaining assessments, no visit window will be applied. Day 29 and Day 113 used in Study day window calculation in the tables below is the respective study day when Week 4 dose and Week 16 dose was received. If that dose is missing, then 29 and 113 is used for respective calculation.

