### **End of Treatment Visit**

Subjects discontinuing treatment prior to week 52 for any reason (see Section [8.1 in protocol](#)) will be asked to complete an End of Treatment visit within a window of  $\pm$  7 days of the next regularly scheduled visit after the last dose of efavaleukin alfa, consisting of all assessments included in the Week 52 visit. If the End of Treatment visit for a subject occurs  $<$  7 days after a progressive disease visit, then the procedures completed at the End of Treatment visit should only be those NOT performed at the progressive disease visit.

Subjects participating in the extended dosing, subjects discontinuing treatment prior to week 102 (Q2W dosing) or week 103 (QW dosing) will be asked to complete an End of Extended Treatment visit within a window of  $\pm$  7 days of the next regularly scheduled visit after the last dose of efavaleukin alfa, consisting of all assessments included in the Week 104 visit.

Subjects participating in the extended dosing, subjects discontinuing treatment after week 104 but prior to week 258 (Q2W dosing) or week 259 (QW dosing) will be asked to complete an End of Extended Treatment visit within a window of  $\pm$  7 days of the next regularly scheduled visit after the last dose of efavaleukin alfa, consisting of all assessments included in the Week 260 visit.

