#### **9.6.5            Physical Measurements**

The analyses will include summary statistics of weight at scheduled time-points and by dose level.

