### Chemistry and Hematology, Weight

Week 1, Day 2	2	2-3
Week 1, Day 8	8	4-12
Week n, Day 7*n+1 (n = 2, 3, 4, 5, 6, 7)	7*n+1	Target day -2, Target day +4
Week 8, Day 57	57	55-71
Week n, Day 7*n+1 (n=12, 16, 20, ..., to 104 in increments of 4)	7*n+1	Target day -13 days, Target day + 14 days
Week 108, Day 757	757	744, 764
Week n, Day 7*n+1 (n=110, ..., to 258 in increments of 2)	7*n+1	Target day -6 days, Target day + 7 days
Week 260, Day 1821	1821	1815, SFU -1 if SFU* is available, otherwise >1814

\*study day corresponding to safety follow-up visit assessment

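### SAP Appendix G has no end-of-treatment analysis visit, so about a third to a half of end-of-treatment laboratory values, and an unclear share of weights, drop out of the by-visit tables

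*SAP*

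**What the plan says.** SAP Appendix G sorts visits after Day 1 into week windows. Safety follow-up keeps its own label ("For Day 1 post-dose visits, and safety follow-up visit, the analysis visit will be same as the scheduled visit"). EOT and progressive-disease visits do not: "Remaining visits (scheduled visit, unscheduled visit, progressive disease visit, or end of treatment visit) after Day 1 for any assessment will be mapped" to a window defined for the assessment in question.

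Two rules then select records. When a window holds more than one non-missing visit, "the visit closest to the target day will be considered for analysis", with ties going to the later one. And "Only visits applicable for that assessment and phase of the study as per the Schedule of Activities tables in the study protocol" are considered for analysis.

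One window table, headed "Chemistry and Hematology, Weight", serves laboratory values and weight. Its main row reads "Week n, Day 7*n+1 (n=12, 16, 20, ..., to 104 in increments of 4"), with each window running from 13 days before target to 14 days after.

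SAP 5.2 and Protocol 9.1.4 place the EOT visit within 7 days either side of the next scheduled visit after the last dose, "consisting of all assessments included in the Week 52 visit".

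SAP 9.6.3.1 summarises laboratory values by time point and also by post-baseline maximum and minimum, worst-grade shifts and a potential Hy's law listing. For weight, SAP 9.6.5 says only: "The analyses will include summary statistics of weight at scheduled time-points and by dose level".

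**The concern.** A subject who stops early for toxicity or worsening cGVHD is measured at the EOT visit. SAP 9.6.1 makes laboratory results and physical measurements part of the primary safety analysis, and cohorts hold 3 to 6 DLT-evaluable subjects, so one or two missing values can change a row. The closest-to-target rule favours the routine sample over the EOT sample whenever the two share a window. A value that was collected because the subject stopped is then set aside because it is not near a nominal week.

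For weight there is a second difficulty. The shared table creates an analysis visit every 4 weeks from Week 12 to Week 104, but the protocol schedules weight only about six times between Weeks 6 and 52 and at Weeks 76 and 104 after that. An EOT weight may therefore be assigned to a week in which no weight is scheduled. Whether it is then summarised depends on how the applicability sentence is read.

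**Working it through.** **Windows.** The plan prints no loss figure to reproduce, but its explicit windows can be checked against the rules. Week 7 (target Day 50) ends on Day 54. Week 12 (target Day 85) starts on Day 85 − 13 = 72. Week 8 must then cover Days 55 to 71, as printed. Week 104 (target Day 729) ends on Day 743 and Week 110 (target Day 771) starts on Day 765, so Week 108 must cover Days 744 to 764, also as printed. There are no gaps or overlaps.

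**Example, QW.** Week 12 sample on Day 85, last dose on Day 92, EOT on Day 99. The Week 12 window is Days 85 − 13 = 72 to 85 + 14 = 99. Distances to target are 0 and 14, so the EOT sample is not used.

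**Example, Q2W.** Last dose at Week 24 (Day 169), EOT at Week 26 (Day 183). The Week 24 window is Days 156 to 183, so EOT loses by 14 days to 0. With a last dose at Week 26, EOT falls on Day 197, the Week 28 target, and is kept.

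**Enumeration.** Assumptions:
- every possible last-dose week from 8 to 48 is equally likely (41 for QW, 21 for Q2W);
- scheduled samples up to the last dose are present and on their target day;
- visits are weekly for QW; for Q2W they are weekly to Week 18, then every 2 weeks (Table 2-2 footnote);
- EOT falls on the next scheduled day, or uniformly within 2 or 7 days of it, and always after the last dose;
- weight is scheduled at Weeks 8, 16, 24, 32, 40 and 52. Table 2-2 is broken in extraction: six marks are clear, but their columns are uncertain by about one.

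For QW with EOT on the scheduled day, a last dose in a target week or the week after it puts EOT in the same window as that week's sample. This applies to Weeks 8, 9, 12, 13, ..., 44, 45 and 48, which is 21 of 41. For weight, 10 of 41 are displaced by a scheduled weight in the same window, and 23 of 41 fall in a window with no scheduled weight (Weeks 12, 20, 28, 36, 44 or 48).

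| Regimen, EOT timing | Labs displaced | Weight displaced | Weight in a week with none scheduled | Weight, sum |
|---|---|---|---|---|
| QW, on the day | 21/41 = 51.2% | 10/41 = 24.4% | 23/41 = 56.1% | 33/41 = 80.5% |
| QW, ±2 days | 41.5% | 19.5% | 57.1% | 76.6% |
| QW, ±7 days | 39.0% | 18.3% | 57.3% | 75.6% |
| Q2W, on the day | 11/21 = 52.4% | 5/21 = 23.8% | 12/21 = 57.1% | 17/21 = 81.0% |
| Q2W, ±2 days | 37.1% | 18.1% | 55.2% | 73.3% |
| Q2W, ±7 days | 34.6% | 17.1% | 54.9% | 72.1% |

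The *Weight displaced* column is the loss if an EOT weight counts in any window. The *Weight, sum* column is the loss if the destination week must have a scheduled weight. If weight were scheduled at Weeks 8, 16, 24, 36 and 52 instead, the two ranges would be about 15% to 20% and 79% to 86%.

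**Weeks 1 to 4.** The laboratory windows for Weeks 2 to 7 are only 7 days wide. For last doses on Days 1 to 29, no EOT laboratory value is displaced with EOT on the scheduled day or within 2 days of it. With the full 7-day allowance the figure is about 19% to 23%.

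**The case against.** *EOT is itself an applicable visit for weight.* It carries all Week 52 assessments, and Appendix G expressly maps EOT into a window table that names weight in its heading. On that reading the weight loss is the smaller figure. This is a fair reading, so a reader who infers that most discontinuation weights are certainly lost goes further than the text allows. The opposite reading is also open, because SAP 9.6.5 confines weight to scheduled time-points. The ambiguity stands.

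*Extreme laboratory values have other routes.* Maximum and minimum, worst-grade shifts and the Hy's law listing are planned, adverse events leading to withdrawal are tabulated, and SAP 9.1 includes unscheduled data unless stated otherwise. This largely answers any claim that the primary safety analysis loses these values. What remains is that Appendix G decides which records are considered for analysis at all, and the SAP does not say whether the extreme-value outputs are exempt. Weight has no maximum or minimum table.

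*The tables are descriptive.* Phase 1b has no statistical hypothesis, the study is ending early, and dose-level reviews use subject-level listings and plots. This limits the consequence and makes the point a low-cost improvement. It does not justify discarding collected values.

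**Conclusion.** The point holds for the by-visit summaries. For last doses in about Weeks 8 to 48, roughly one third to one half of EOT chemistry and hematology values are displaced by an on-schedule sample in the same window, however the applicability sentence is read. For weight the loss is about 17% to 24% or about 70% to 80%, depending on a reading that the SAP leaves open and on weight weeks assumed from a broken table. All figures assume evenly spread stopping times and on-target scheduled samples.

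Three stronger inferences are not supported:
- **Bias toward no effect.** In the Week 12 example the subject's Day 85 on-treatment value stays in the row. The displaced Day 99 value, 7 days after the last dose, could be worse or already recovering. The direction is not established.
- **DLT stoppers.** DLTs fall in the first 4 weeks, where windows are narrow, so the Weeks 8 to 48 figures do not describe them.
- **Vital signs and progressive-disease visits.** The mapping rule covers them too, but no loss was computed for either.

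**What to change.** In SAP Appendix G:

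1. Add an *End of treatment* analysis visit for chemistry, hematology and weight, labelled directly as safety follow-up already is. It takes each stopping subject's EOT or end-of-extended-treatment value, or the progressive-disease-visit value where the procedure was not repeated at EOT (Protocol 9.1.4 allows this when the two visits are less than 7 days apart). Show value and change from baseline by dose level beside the week rows.
2. State that the closest-to-target and Schedule of Activities rules select records for the week rows only, and that the maximum/minimum, worst-grade shift and Hy's law outputs use all post-baseline records.

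With a label of its own, no EOT value can be displaced by a week sample, and the weight ambiguity no longer affects whether the value is shown. The cost is SAP wording and one extra row per table. No new data are needed and no clinical rule changes.

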### **Study Visit**

Since the actual visit for a subject may not exactly coincide with their scheduled visit date, the actual visit date is mapped to the analysis visit as per the analysis visit windows described in [Appendix G](#).

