## **9. Statistical Methods of Analysis**

### **9.1 General Considerations**

Standard descriptive statistics will be provided. All binary endpoints will be summarized using the number and percentage of subjects. All continuous endpoints will be summarized using descriptive statistics including mean, standard deviation, minimum, maximum, and number of non-missing observations (n). Summaries will be provided at all scheduled time-points unless specified otherwise. Data collected at unscheduled visits or time-points will be included in the analysis unless stated otherwise. **All safety and efficacy analyses will be performed using the Safety Analysis Set based on subject's actual treatment received.**

Only critical subject-level data listings will be provided in the clinical study report.

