### **9.6.3            Laboratory Test Results**

#### **9.6.3.1        Chemistry and Hematology**

The analyses of safety laboratory endpoints will include summary statistics of baseline, post-baseline lab values at all the time points, change from baseline to post-baseline, post-baseline maximum/minimum and change from baseline to post-baseline maximum/minimum by dose level.

Shifts tables indicating the change between the baseline and the worst post dose CTCAE grades based on CTCAE version 4.03 or later will be provided for selected laboratory parameters of interest. Subject incidence of worst post-baseline eosinophils counts by the laboratory normal range will be provided.

**Chemistry and hematology laboratory tests performed by local laboratories will be included in the analyses where applicable in cases where central laboratory values were not obtainable (i.e. due to Covid restrictions).**

A listing of subjects identified as potential Hy's law cases (ALT or AST of >3xULN associated with total bilirubin > 2xULN and ALP <2xULN at a visit) will be provided with relevant laboratory tests included in the listing.

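### The SAP's central-over-local laboratory rule is not limited to by-visit summaries, so read literally it can drop local hepatotoxicity re-tests from liver maxima and the Hy's law listing

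*SAP*

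**What the plan says.** SAP Appendix G assigns records to analysis visits. "Remaining visits (scheduled visit, unscheduled visit, progressive disease visit, or end of treatment visit) after Day 1 for any assessment will be mapped" to a window, and "Data collected through central lab and local lab will both be mapped into analysis visit windows". It then states: "The local lab data can only be used in analysis when there is no central lab data available in the analysis visit window". If several records remain in a window, the one closest to the target day is used.

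SAP 9.6.3.1 plans post-baseline maxima and minima, shifts from baseline to the worst CTCAE grade, worst eosinophil category and a Hy's law listing. On local laboratories it says only that chemistry and hematology tests "performed by local laboratories will be included in the analyses where applicable in cases where central laboratory values were not obtainable", giving Covid restrictions as the reason. The shift tables "will be provided for selected laboratory parameters of interest", and those parameters are not named. The Hy's law criterion is ALT or AST above 3x ULN "associated with total bilirubin > 2xULN and ALP <2xULN at a visit".

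SAP 9.1 adds: "Data collected at unscheduled visits or time-points will be included in the analysis unless stated otherwise".

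On the protocol side, Appendix 2 makes the central laboratory the default for on-study chemistry and lists hepatotoxicity monitoring as an exception. Appendix 7 has those additional assessments done locally, asks for a repeat within 24 hours, and asks for re-testing every 24 hours when TBL exceeds 2x ULN or INR exceeds 1.5. It also requires the laboratory results of a potential DILI event on the CRF.

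**The concern.** The usual sequence in a liver event is a raised central value at a scheduled visit, followed by local re-tests over the next days. The peak may well be among the re-tests. The protocol collects these values, but the Appendix G sentence, read as it stands, removes them from analysis because the central trigger occupies the same window.

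Any resulting error runs one way. Dropping results can lower a maximum or a worst grade but never raise it, and it can miss a subject who meets the Hy's law thresholds. SAP 9.6.1 makes laboratory summaries part of the primary safety analysis, and SAP 9.1 promises only critical subject-level listings in the report, so a reader may have no other table that shows the local peak.

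**Working it through.** The plan gives no figure to reproduce here. The check has three parts.

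**1. Is there an exemption?** Appendix G contains none for worst-value outputs. SAP 9.6.3.1, which defines those outputs, also contains none and repeats the substitute role of local results. The general inclusion of unscheduled data in SAP 9.1 gives way wherever the SAP states otherwise, as Appendix G does for local data. Appendices E and F are not visible in the public copy, so this covers visible text only.

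**2. How often does a local repeat share the trigger's window?** Inputs are the chemistry windows in SAP Appendix G:

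- Weeks 2 to 7: target day -2 to +4, which is 7 days.
- Week 8: days 55 to 71, which is 17 days.
- Weeks 12, 16, ..., 104: target day -13 to +14, which is 28 days. There are (104 - 12)/4 + 1 = 24 such windows, 11 of them up to week 52. The other 13 concern extended-dosing subjects only.

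The windows are contiguous. If the trigger falls on any day of a window of width w and the repeat comes k days later, both lie in that window on w - k of the w trigger days.

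| Windows | k = 1 day | k = 3 days |
|---|---|---|
| Weeks 2 to 7 (w = 7) | 6 of 7 | 4 of 7 |
| Week 8 (w = 17) | 16 of 17 | 14 of 17 |
| Weeks 12 to 104 (w = 28) | 27 of 28 | 25 of 28 |

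The second column allows for time until the central result is known, because protocol Appendix 7 does not say when the 24 hours start. In weeks 12 to 104, a trigger within 3 days of target (the widest visit window in protocol 9.1.2) plus a 3-day lag ends no later than day +6, inside the limit of +14. Near-target draws therefore still share the window. Where daily re-testing applies, an on-target draw shares its window with the next 14 daily re-tests in weeks 8 to 104, and with the next 4 in weeks 2 to 7.

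Calendar coverage: the 28-day windows start on day 72. Days 72 to 365 are 294 of the 364 days from day 2 to day 365, or 81%.

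**3. What is lost?** A hypothetical subject with normal baseline values, not taken from the documents, in multiples of ULN:

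| Record | ALT | TBL | ALP | All three criteria met? |
|---|---|---|---|---|
| Central trigger | 3.5 | 1.8 | 1.5 | No |
| Local, next day | 6 | 2.4 | 1.6 | Yes |

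Under the literal rule, maximum ALT is 3.5 and maximum TBL is 1.8, and the subject is not listed unless a later central record qualifies. With all results used, the maxima are 6 and 2.4 and the subject is listed. If central TBL had been 2.1, the subject would be listed either way and only the peak would be understated.

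**The case against.** The strongest reply is that the sentence was never meant to reach worst-value outputs. The SAP's Study Visit definition gives the purpose of the windows: "the actual visit date is mapped to the analysis visit as per the analysis visit windows described in" Appendix G. The local-laboratory sentence stands beside the closest-to-target rule, and both can be read as choosing one record to represent a visit. If the closest-to-target rule governed every output, it would also strip unscheduled central values from the maxima and leave the SAP 9.1 inclusion rule little to do. The Hy's law criterion refers to a visit, not an analysis visit, and a local re-test can itself be an unscheduled visit. This makes the by-visit reading plausible, but no visible text adopts it, and SAP 9.6.3.1 restricts local chemistry in the very section that plans these outputs.

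The trigger for the repeat also has limits. Appendix 7 applies close observation to subjects whose treatment is withheld for potential DILI, and to AST or ALT above 3x ULN, or a 2-fold rise over baseline for subjects elevated before drug. For phase 1b values attributed to cGVHD, protocol 7.4.3 refers management to the Medical Monitor. A reader should not infer that every elevation above 3x ULN leads to a next-day local repeat.

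Preferring central results is a sound way to avoid mixing assays in by-visit summaries. The practical stakes are also modest: the study is ending early, about 30 escalation subjects were planned, the analysis is descriptive, and concurrent aminotransferase and TBL or INR elevations meeting the Appendix 7 criteria are reported as serious adverse events within 24 hours.

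**Conclusion.** The rule is worded too broadly. Followed literally, it can understate liver maxima and worst grades, the latter only if liver tests are among the selected parameters. It can also omit a subject from the Hy's law listing when no central record meets all three criteria. Confidence is medium because by-visit use may be what was intended; severity is minor to moderate.

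Three stronger readings are tempting and not supported:

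- That the plan certainly excludes local peaks. The text permits that result but does not settle it.
- That 81% is a chance of losing a case. It is calendar coverage of the 28-day windows. A loss also needs a local value worse than every usable central one, and the documents give no frequency for that.
- That a liver signal would be hidden from the sponsor. Serious adverse event reporting, adverse event tables (including the hepatic event of interest) and the dose level review listings do not depend on this rule. They do not, however, correct the laboratory maxima or the listing.

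The overlap counts assume a central trigger and a repeat one or three days later. Local results in windows without a central value stay usable.

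**What to change.** State in SAP Appendix G and 9.6.3.1 that the central-first and closest-to-target rules apply to by-visit summaries only. State also that post-baseline maxima and minima, worst-grade shifts, worst eosinophil category and the Hy's law listing use all post-baseline results, central and local, scheduled and unscheduled, each judged against its own laboratory's reference range. Add a footnote that these outputs mix assays.

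The cost is two or three sentences and a programming flag, with no change to trial conduct. The drawbacks are that local reference ranges must be on file and that worst-case tables combine central and local assays. If the programs already use all data for these outputs, the change only records that.

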7.4.2.1.1 Phase 1b

Dose adjustment of efavaleukin alfa for individual subjects is not allowed until the [REDACTED] is determined. The Medical Monitor should be informed of withholding of efavaleukin alfa for acute clinical events such as acute infection or major surgery. Once the [REDACTED] dose is determined, all phase 1b subjects may continue study therapy at the [REDACTED] dose and frequency (at the discretion of the Sponsor, following discussion and agreement between the principal investigator and medical monitor) and will be subject to the dose adjustment guidelines in Section 7.4.2.1.2. A subject experiencing worsening of cGVHD that requires the addition of new immunosuppressive medication(s) at any time during the study or initiation of an increase in systemic corticosteroid dose above baseline after week 4 of the study (at the discretion of the treating investigator) will be deemed a treatment failure. These subjects will discontinue treatment and will have a safety follow-up visit (see Section 9.1.5).

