**PD assessments include but are not limited to:**

[REDACTED]

[REDACTED]

[figure not shown]
[REDACTED] Due to the skewed distribution of PD data, mean, standard deviation and standard error will be estimated based on log-transformed data, and the estimates will be back-transformed and presented, which are equivalent to geometric mean, geometric standard deviation and geometric standard error.

To maintain the integrity of PD results, data collected at an end of treatment or end of extended treatment visit which is completed outside the upper limit of protocol defined window (> 9 days after the last dose date for QW cohorts and > 16 days for Q2W cohorts) will not be included in the analysis. In addition, data collected at a visit after skipping one or more consecutive doses prior to that visit will be also excluded from analysis (the same window will be used as above i.e. (> 9 days after the last dose date for QW cohorts and > 16 days for Q2W cohorts).

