### Vitals

Analysis Visit	Target Day	Study Day Window
----------------	------------	------------------

Week 1, Day 2	2	2
Week 1, Day 3	3	3
Week 1, Day 4	4	4-6
Week 1, Day 8	8	7-9
Week 1, Day 11	11	10-12
Week n, Day 7*n+1  (n = 2, 3, 4, 5, 6, 7, 8, 9, 10, 11, 12, 13, 14)	7n+1	Target day -2, Target day +4
Week 15, Day 106	106	104, Day 113-3
Week 16, Day 113 Pre-dose	113	Day 113-2, Day 113
Week 16, Day 114	114	Day 113 + 1
Week 16, Day 115	115	Day 113 + 2
Week 16, Day 116	116	Day 113 + 3
Week 17, Day 120	120	Day 113 + 4, 124
Week 18, Day 127	127	125-131
Week 20, Day 141	141	132-148
Week n, Day 7*n+1  (n = 22, 24, 26,.. to 258 in increments of 2)	7n+1	Target day -6, Target day +7
Week 260, Day 1821	1821	>1814

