### Pharmacodynamic assessments

Week 1, Day 2	2	2-3
Week 1, Day 4	4	4-6
Week 1, Day 8	8	7-9
Week 1, Day 11	11	10-12
Week 2, Day 15	15	13-19

Week 3, Day 22	22	20, Day 29 - 3
Week 4, Day 29	29	Day 29 -2, Day 29
Week 4, Day 30	30	Day 29 +1
Week 4, Day 32	32	Day 29 + 2, Day 29 +4
Week 5, Day 36	36	Day 29 + 5, 40
Week n, Day 7*n+1 (n = 6,7,8,9,10,11)	7*n+1	Target day -2, Target day +4
Week 12, Day 85	85	83, 92
Week 14, Day 99	99	93, Day 113 -7
Week 16, Day 113	113	Day 113- 6, Day 113
Week 16, Day 114	114	Day 113 +1
Week 16, Day 116	116	Day 113+ 2, Day 113 +4
Week 17, Day 120	120	Day 113 +5, 124
Week 18, Day 127	127	125- 134
Week n, Day 7*n+ 1 (n= 20, 22, ..to 50 in increments of 2 )	7*n+1	Target day -6 days, Target day + 7 days
Week 52, Day 365	365	359-379
Week n, Day 7*n+ 1 (n= 56, 60, 64, ..., to 104 in increments of 4)	7*n+1	Target day - 13 days, Target day + 14 days
Week 108, Day 757	757	744, 764

Week n, Day $7^*n+1$ (n=110, ..., to 258 in increments of 2)	$7^*n+1$	Target day -6 days, Target day + 7 days
Week 260, Day 1821	1821	>1814

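### When the Week 4 dose is not given, SAP Appendix G still files a Day 30 pharmacodynamic sample as a day-after-dose value, and the skipped-dose limits in SAP 9.7.1.2 do not remove it (minor)

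*SAP*

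**What the plan says.** Appendix G of the SAP assigns records to analysis visits. For the dose-anchored windows, the Day 29 or Day 113 used in the calculation "is the respective study day when Week 4 dose and Week 16 dose was received". The fallback follows: "If that dose is missing, then 29 and 113 is used for respective calculation".

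In the PD table, Week 4, Day 30 is the anchor plus 1 day, and Week 4, Day 32 is "Day 29 + 2, Day 29 +4". Week 16, Day 114 and Day 116 are built the same way on Day 113. In the vital signs table, "Week 16, Day 114" and the two visits after it are the Week 16 anchor plus 1, 2 and 3 days. Week 4 vital signs use a fixed window with no dose anchor.

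Two rules decide which records enter. The first is wide: "Remaining visits (scheduled visit, unscheduled visit, progressive disease visit, or end of treatment visit) after Day 1 for any assessment will be mapped" to these windows. The second narrows it: "Only visits applicable for that assessment and phase of the study as per the Schedule of Activities tables in the study protocol" are considered.

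SAP 9.7.1.2 also excludes PD data from a visit that follows one or more skipped doses. It puts that into practice with the limits "> 9 days after the last dose date for QW cohorts and > 16 days for Q2W cohorts". SAP 9.6.4 states no such exclusion for vital signs.

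A dose can be absent without the subject leaving the study. Protocol 7.4.2.1.1 refers to "withholding of efavaleukin alfa for acute clinical events such as acute infection or major surgery".

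**The concern.** The visits one to four days after the anchor are separate from the weekly visits because they follow a dose. Protocol Table 2-1 sets out the columns after the Day 29 dose in hours after dosing. If there was no dose at that visit, a record on Day 30 is a late trough value, yet the fallback gives it the same label as the day-after-dose samples of the other subjects. Nothing in Appendix G leaves the visit empty in that case.

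At stake is the by-visit PD summary, which is a geometric mean in cohorts planned at 3 to 6 DLT-evaluable subjects, so one mislabelled record carries visible weight. A reader of the table could not see that it mixes dosed and undosed subjects.

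**Working it through.** The plan states no figure on this point, so there is none to reproduce. The check applies the Appendix G windows and the 9.7.1.2 limits to each sample day.

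**Inputs.** The anchor defaults to Day 29. The previous dose is nominally Day 22 for weekly (QW) dosing (29 − 7) and Day 15 for two-weekly (Q2W) dosing (29 − 14). It is varied by ±1 day, the visit window through Week 4 in Protocol 9.1.2. A record is excluded if days since last dose exceed 9 (QW) or 16 (Q2W).

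**Week 4 dose not given, previous dose on time.**

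| Sample day | PD analysis visit | QW: days since Day 22 | Q2W: days since Day 15 | 9.7.1.2 limits |
|---|---|---|---|---|
| 30 | Week 4, Day 30 | 8 | 15 | kept |
| 31 | Week 4, Day 32 | 9 | 16 | kept |
| 32 | Week 4, Day 32 | 10 | 17 | excluded |
| 33 | Week 4, Day 32 | 11 | 18 | excluded |

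**Previous dose one day early or late.** Day 30 becomes 9 or 7 days (QW) and 16 or 14 days (Q2W), so it is kept in every case. Day 32 becomes 11 or 9 days (QW) and 18 or 16 days (Q2W), so it is kept only if the previous dose was late. If two consecutive doses were missed, Day 30 is 15 days (QW, 30 − 15) or 29 days (Q2W, 30 − 1) after the last dose and is excluded.

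**Week 16.** With the previous dose on Day 106 (QW) or Day 99 (Q2W), Day 114 is 8 or 15 days later (kept) and Day 116 is 10 or 17 days later (excluded). Vital signs on Days 114, 115 and 116 would all be kept. This is conditional: Table 2-2 as available goes from Day 113 to Day 120, and Appendix G counts only visits in the Schedule of Activities.

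**How a Day 30 record can arise.** A subject whose dose is withheld may still attend, or may have an unscheduled sample. For a QW subject who stops after Day 22, Protocol 9.1.4 puts the end-of-treatment visit within ±7 days of the next scheduled visit. That is Day 29, so the range is Days 22 to 36 and includes Day 30. The end-of-treatment limit in 9.7.1.2 is the same 9 days and does not exclude it.

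**Size, illustration only.** Let r be the ratio of the day-after-dose value to the trough. The documents do not give r. If one of n subjects contributes a trough value, the geometric mean falls by 1 − r^(−1/n). For r assumed between 1.25 and 3, this is 4% to 17% with n = 6 and 7% to 31% with n = 3. It is zero at r = 1 and changes sign if r is below 1.

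**The case against.** The strongest reply is that 9.7.1.2 already deals with this. Its wording covers any PD visit after a skipped dose, and a Day 30 sample after a missed Week 4 dose fits that description. The same sentence, however, applies the exclusion through day limits, and a program coded to those limits keeps Day 30. The words and the numbers disagree, which is itself a reason to amend the text.

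Other parts of the reply stand and narrow the point:

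- A reader might infer that the whole set of samples from 24 to 72 hours is mislabelled. For PD on the nominal schedule it is not, because the Day 32 and Day 116 samples are excluded.
- A reader might infer that these subjects had no preceding dose. They had one about 7 or 14 days earlier; what is missing is a dose at that visit.
- A reader might extend the point to Week 4 vital signs. Their window is fixed at Days 27 to 33 and has no post-dose visits. The chemistry, hematology and antibody windows do not use the anchor either, and pharmacokinetic parameters use actual dosing and sampling times.
- The trigger is narrow: a missed dose and a PD record on a particular day. The number of such subjects is not given and is probably small.
- No primary endpoint is affected. Phase 1b has no statistical hypothesis, and the maximum and minimum summaries of vital signs do not depend on these visit labels.

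**Conclusion.** The point holds in a limited form. For a subject without the Week 4 dose, the fallback anchor together with the 9- and 16-day limits places a Day 30 PD record in a post-dose summary where it does not belong. This follows from the stated rules for both regimens, and a one-day shift in the previous dose does not change it. It assumes that the day limits, not the wider wording of 9.7.1.2, govern the programming, and that exactly one dose was missed.

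The Week 16 part, including everything on vital signs, depends on whether Days 114 to 116 were in the schedule in force. The documents as available do not show that they were.

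It is tempting to conclude that the acute Treg or heart-rate response is biased toward no effect by a known amount. The documents do not support that. They give no ratio of day-after-dose value to trough, Protocol 5.4 describes the conventional T-cell (Tcon) increases as minimal, and the heart-rate finding reported in Protocol 3.2.2.1 comes from monkeys. The mislabelling is established; its size and direction are not. Severity: minor.

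**What to change.** In Appendix G, replace the fallback sentence with text to this effect: if the Week 4 (Week 16) dose was not given, the dose-anchored post-dose analysis visits are not populated for that subject. These are PD Days 30, 32, 114 and 116 and, where the schedule contains them, vital signs Days 114 to 116. Nominal Day 29 or 113 is then used only to bound the adjacent weekly windows. State also that such records stay unassigned and are listed, so that they do not drift into the Week 16 pre-dose visit, which is another dose-relative label.

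In 9.7.1.2, reconcile the skipped-dose wording with the day limits, so that a PD sample following a skipped dose is kept out of the post-dose summaries whatever the day count.

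The cost is two sentences and one programming condition before the final analysis. The records stay in the database and leave only the by-visit summaries they do not fit.
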